The lactobacilli are absorbed via the intestinal cells, and the intestine has, as described, its own microbiome. It is therefore important to monitor any changes in intestinal microbiome during treatment with vaginal lactobacilli. Vagina is not sterile and is also home to its own bacteria. The physical relationships between the bladder and vagina are close, and it is therefore important to be able to assess any possible impact of the vaginal microflora on the urinary microbiome.

Once the possible physiological, gynecological, and urological causes have been clarified and if necessary treated, there is currently no evidence-based well-documented treatment options for women with rUTI.

Our hypothesis is that postmenopausal women with rUTI have a decreased amount of lactobacillus in their bladder, and that treatment with *Lactobacillus rhamnosus* and *Lactobacillus reuteri*, in the form of capsule Femidur, will affect the urinary microbiome with an increased number of Lactobacilli in the bladder and vagina and thus decrease the number of UTI. Monitoring both the urine and vagina microbiome is therefore necessary.

Protocol

We also want to monitor the gut microbiome to see if they are altered by the uptake of lactobacilli, and whether this change follows the eventual change in urinary microbiome change and whether this might have an impact on the number of UTI.

The urinary microbiome between individuals is very different, whereas in the same woman it is stable over time unless she gets a urinary tract infection. It is therefore important to be able to compare the urinary microbiome of the same woman both during placebo and active treatment. In addition, a more accurate study of the bacterial composition on the individual women is possible when the women develop a urinary tract infection.

The women's urine microbiome is checked already after a month and a half. This is to get an idea of how quickly any change in the urine microbiome occurs and whether there is a difference between the individual women participating in the study.

Purpose of the project

The primary objective of the study is to describe the composition of the urinary microbiome in postmenopausal women with rUTI before and after treatment with *Lactobacillus rhamnosus* and *Lactobacillus reuteri*.

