Secondarily to investigate whether treatment with *Lactobacillus rhamnosus* and *Lactobacillus reuteri* has a preventive effect on rUTI in postmenopausal women. In addition, whether the intestinal microbiota is affected by treatment with *Lactobacillus rhamnosus* and *Lactobacillus reuteri* and whether differences in the vaginal microbiome have an impact on the above

Method

Study design

[figure not shown]
The study program is designed as a prospective, double-blind, randomized case-cross over study. The study program last 6 months.

The women are randomized to the treatment group (capsule Femidur containing two types of lactobacilli) and to the control group (placebo capsule). After three months, the women cross, and the group that received treatment now receives a placebo and vice versa. The women remain blinded throughout the period for both themselves and the staff.

Randomizing

Randomization of the women takes place by extraction in the electronic system RedCap where the woman's grouping in the study is determined. The woman is anonymized in the study by linking her CPR number to a study number. The tests she submits during her studies are linked to this number. After randomization and submission of samples and questionnaire, the capsules (Femidur® or placebo) are dispensed.

Overview of project progress:

Study Setup and intervention

The included women are divided into two groups. Women in both groups fill out the drinking and water-diary (DWD) over 3 days as well as the ICIQ-OAB and ICIQ-UI-SF questionnaires. A freshly loaded urine sample, a vaginal swab from the top of the vagina and a stool sample are then delivered. The vaginal swab can be taken by the patient himself, or by the doctor/nurse. The urine sample is freshly loaded mid-stream urine. The stool sample can be taken at home and stored up to 7 days in a regular freezer.

The women are then given the capsules, which they take every day for 3 months.

After 1.5 months, all the women show up in the outpatient clinic where urine samples and vaginal swabs are made, and stool samples are delivered. The women fill out the ICIQ-OAB and ICIQ-UI-SF questionnaires.

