After 3 months, the women meet again. They hand in a stool sample they bring from home and do a urine sample and a vaginal swab in the outpatient clinic. They completed questionnaires like those filled in at the beginning, but only DWD for a period of one day. Capsules (Femidur or placebo) are again dispensed for the next three months. There has now been cross-over in the study, and the women who used to receive placebo now receive Femidur and vice versa. The women are still blinded, and it is not known who gets what.

The women meet again after 4.5 months, and a urine sample and a vaginal swab are performed. Stool sample is handed in. They fill out the ICIQ-OAB and ICIQ-UI-SF questionnaires.

Protocol

After six months, the women meet for the last time. They bring a stool sample and a DWD for one day. In the outpatient clinic, they do a urine test and a vaginal swab. They fill out the ICIQ-OAB and ICIQ-UI-SF questionnaires. The effect of the treatment with capsule Femidur is assessed, and it is agreed with the woman whether she has finished treatment for the problem rUTI or whether she should return to the gynecological outpatient clinic for further examination.

If the women develop symptoms of UTI during the project, the women should contact their general practitioner or the emergency medical service to have their urine examined (regular U-stix and culture). In connection with the study, the women are given a card for display, which says that they are participating in a trial, and we ask that the urine is not only tested with regular U-sticks but is also sent for cultivation. If the women develop culture-verified UTI during the study period, the women are treated based on the urine culture response. The treatment is initiated by a doctor or emergency physician. Does the woman have UTI when she comes to the outpatient clinic, the treatment is initiated there.

Implementation, examination and extend of study

All women who are referred to the gynecological outpatient clinic or urological outpatient clinic with rUTI receive the examination usually done for their specific condition, at the first visit to the outpatient clinic.

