Some of the women will already be treated with topical estrogen initiated by their general practitioner. For those women who are already being treated with topical estrogen, this is continued. For the women with a wish to participate in the study, it is noted in the project papers whether the woman is taking estrogen and whether it is topical or systemic treatment. If the woman enters the trial and are not already undergoing estrogen therapy, a possible start-up is awaited until after the end of the trial.

At the inclusion data on height, weight, tobacco and alcohol consumption, drug status, parity, previous cancers, diseases, and operations in the abdomen as well as constipation is collected. Information from the journal of the women is not used for the study.

If the woman has rUTI, she is informed about the trial and offered written material as well as a call for further information.

Standards

Femidur® is produced by Pharmaforce, a Danish company founded in 2005. Femidur® capsules are made from gelatin from plants, as well as maltodextrin. Femidur® contains 2 vaginal lactic acid bacteria; Lactobacillus rhamnosus GR-1® and Lactobacillus reuteri RC-14®, both of which can colonize the vagina after oral ingestion. Femidur® contains 5 billion vaginal lactic acid bacteria per capsule of Femidur®. Femidur® capsules should be swallowed whole.

The women are given capsules Femidur® once. It is either at startup or after three months, dependent on the randomization.

The placebo capsules will match Femidur® in appearance. The placebo capsules consist primarily of gelatin from plants and maltodextrin.

The distribution of capsules is planned to avoid the case where the women have capsules with both placebo and Femidur at home at the same time and may mix the two.

Statistical considerations

Number of patients for inclusion

To our knowledge, no previous studies have been conducted on lactobacilli and their possible impact on the urinary microbiome. The number of women to be included to achieve a sufficient number in relation to strength calculation is therefore difficult to estimate. There are other studies available on the vaginal microbiome and disease, and based on these¹⁸, it is planned to include 100 women in total.

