Previous studies on postmenopausal women have shown a very small drop-out rate and a high inclusion rate¹⁹, which is why it is expected that the required number of women can be included within a limited period. The inclusion period will continue until the 100 women are included. If there are drop out during the first 3 months, a similar number to the drop out will be included until there is a total population of 100 women.

Statistical variables and data

Variables that are compared between the groups are operational taxonomic unit (OTU) richness (number of unique bacteria) and Shannon Index (the distribution of the bacteria in the sample) and expressions of alpha diversity. Beta diversity, which expresses how bacterial composition varies between samples, is assessed using PCA plots with Hellinger transformation or Principal Bray-Curtis. Heatmaps are used for further assessment of differences and similarities.

Numerical parametric data is given as mean +/- SD while non-parametric data is given as median and range. IBM SPSS Statistics 22 and R (the R foundation) will be used for statistical analysis. The data material will contain demographic data (age, smoking status, births, etc.) and the composition of the microbiome in the vagina, bladder and intestines will be used. Data that will undergo analysis is descriptive patient data, the urine-microbiome and its composition, vaginal and gut microbiome composition and results around rUTI. For all variables, p-values will be calculated and values <0.05 are significant.

Subjects

The women included in the study must be postmenopausal and with a minimum of 3 years of menostasis. If the women have undergone hysterectomy before menopause, the woman must be at least 60 years old when they are included. The women must be diagnosed with rUTI.

The diagnosis of rUTI is made by either:

- (a) Three cultivation-verified UTI in a year, or
- (b) Two cultivation-verified UTI over the course of six months.

If the woman is diagnosed with rUTI, a positive culture response will be checked before the woman arrive at the outpatient clinic. If there are no culture responses in the hospital's medical record system, contact is

[figure not shown]
Protocol

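### The plan calls p<0.05 significant for every variable, names no primary urinary index or test, states no adjustment and labels nothing exploratory.

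*Combined protocol and SAP*

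**What the plan says.** - **Significance rule** (Statistical variables and data): "For all variables, p-values will be calculated and values <0.05 are significant". The sentence before it lists the data to be analysed: patient data, the urinary, vaginal and gut microbiomes, and results on recurrent UTI. OTU richness, Shannon index and other alpha-diversity measures stand side by side as variables compared between the groups. Beta diversity is assessed by one of two alternative plots. Software is named; a test or model is not.
- **Objectives** (Purpose of the project): the primary objective is to "describe the composition of the urinary microbiome in postmenopausal women with rUTI before and after treatment". The secondary objectives start with whether treatment "has a preventive effect on rUTI in postmenopausal women", followed by the gut and vaginal microbiomes.
- **Contrast**: the background, just before the objectives, says "It is therefore important to be able to compare the urinary microbiome of the same woman both during placebo and active treatment". The Research ethics section also treats the women as their own controls.
- **Hypothesis** (background): treatment leads to "an increased number of Lactobacilli in the bladder and vagina" and so to fewer UTIs.
- **Visits** (Clinical tests, sampling of biological material): baseline and months 1.5, 3, 4.5 and 6. The background gives the sample at a month and a half its own purpose, which is to see how fast any change occurs.
- **Sample size** (Number of patients for inclusion): 100 women, with the remark "The number of women to be included to achieve a sufficient number in relation to strength calculation is therefore difficult to estimate".

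**The concern.** The ranking of objectives tells a reader that gut, vaginal and UTI results are not primary. It does not say what answers the primary objective. Composition is not a single variable: richness may move while Shannon index does not, and neither one measures lactobacilli, which the hypothesis is about. The contrast is also worded in more than one way: before versus after treatment in the objective, between the groups in the statistical section, and within the same woman in the background.

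Two things follow. The urinary index and the comparison reported as the main result can be picked once the data are known. And the rule gives every p<0.05 the same status, so a chance finding in the gut or vaginal data would be called significant in the same terms as the urinary result. A reader of the publication could not tell which claim had been planned.

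**Working it through.** The plan gives no error rate, list of tests, effect size or power, so it has no figure of its own to reproduce. The only design figure is 100 women, which can be neither confirmed nor refuted.

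**Inputs from the plan.** Threshold 0.05 per variable (taken as two-sided, which the plan does not state); two named alpha-diversity indices; three sampled sites; UTI results.

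**Assumptions.** One contrast; one test per index and site; at most one UTI test; normal test statistics with a common correlation ρ. The plan gives neither the number of tests k nor ρ, so a range is shown.

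**Formula.** With independent tests, P(at least one p<0.05) = 1 − 0.95^k:
- k = 2: 1 − 0.95² = 0.0975
- k = 6 (2 indices × 3 sites): 1 − 0.95⁶ = 0.265
- k = 7 (plus one UTI test): 1 − 0.95⁷ = 0.302

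With common correlation ρ, the same probability comes from numerical integration over the shared component:

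| Tests | ρ = 0 | 0.5 | 0.7 | 0.8 | 0.9 |
|---|---|---|---|---|---|
| 2 | 0.098 | 0.091 | 0.083 | 0.078 | 0.070 |
| 6 | 0.265 | 0.207 | 0.164 | 0.139 | 0.108 |
| 7 | 0.302 | 0.230 | 0.178 | 0.149 | 0.114 |

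**A structured case.** Suppose the sites are independent of each other, the two indices correlate at 0.9 within a site, and the UTI test is independent. The chance per site is 0.0704.
- 6 tests: 1 − (1 − 0.0704)³ = 0.197
- 7 tests: 1 − (1 − 0.0704)³ × 0.95 = 0.237

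**Reading.** For the primary aim alone (two urinary indices, one contrast) the chance is 7-10% instead of 5%. Over three sites, without or with a UTI test, it is 11-30%, or 20-24% in the structured case. Further diversity measures, tests on single taxa or patient characteristics would add to this. Women also complete questionnaires ("They fill out the ICIQ-OAB and ICIQ-UI-SF questionnaires"). Their scores are not in the list of data for analysis, so they are not counted here.

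**The case against.** The strongest reply is that the primary aim is to describe, the plan makes no power claim, and beta diversity is judged from plots. Strict error control would then be out of place. This stands in part, and it is why the fix includes a route that changes wording only. It does not rescue the sentence: a purely descriptive plan would not declare significance for every variable, and this one also has a directional hypothesis and a prevention aim.

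Several stronger readings are tempting but not supported:
- *That the sponsor has decided against any correction.* The text is silent. What can be said is that no adjustment is stated.
- *That there is no hierarchy.* The objectives are ranked. The 11-30% range pools primary and secondary variables; for the primary aim alone the excess is modest.
- *That visit and contrast are wholly open.* The purpose given to the 1.5-month sample points to the end of each period as the main time, and the background favours Femidur versus placebo within woman. The gap lies mainly in the index and the test, with inconsistent wording of the contrast.
- *That counting every visit and contrast gives much higher error rates.* Contrasts within a woman share samples, so they cannot be treated as extra independent tests, and the plan does not say how many would be run. No such figure is used here.

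Washout, carry-over and the precision of 100 women are separate topics and play no part in this point.

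**Conclusion.** The point holds and should be acted on. The rule as written covers all variables, and the supplied text names no primary urinary index, no test, no adjustment and no exploratory label. With no true effect, the chance of at least one result called significant at a single contrast is 7-10% for two urinary indices and 11-30% for six or seven tests over three sites. These sizes rest on assumed test counts and correlations. The direction does not: with two or more tests that are not perfectly correlated, the chance exceeds 5%. Randomization, blinding and data collection are unaffected; what suffers is how a reported p-value can be read.

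**What to change.** Replace the quoted sentence with a short paragraph, agreed before unblinding, that does the following:

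1. Names one primary urinary variable. OTU richness and Shannon index are already in the plan. Lactobacillus relative abundance is closer to the hypothesis, but it is a proportion, not a count, and can rise with no rise in the number of lactobacilli; the text should say so.
2. Names one contrast, Femidur versus placebo within woman at the end of each period (months 3 and 6), and one two-sided test at 0.05 from a model with treatment, period and woman. The objective and the statistical section should then use the same wording.
3. Names culture-verified UTIs per period as the key secondary outcome, reported as a rate ratio with 95% confidence interval.
4. Reports all other variables as exploratory, with estimates and false-discovery-rate adjustment, and makes no significance claims for baseline patient data.

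If the sponsor regards the aim as purely descriptive, the simpler course is to delete the blanket significance rule and label all p-values exploratory.

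**Cost.** No new samples or visits: the sequencing and cultures are already planned. The first route takes one paragraph and one sponsor decision; the second takes wording only. The downside is that fewer results can be called significant, and that the 100 women were not sized for whichever variable is named.

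### No within-woman Femidur–placebo contrast with a confidence interval is planned, so a non-significant result could be misread as no effect

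*Combined protocol and SAP*

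**What the plan says.** The analysis plan is the short section headed Statistical variables and data.

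- **Comparisons.** "Variables that are compared between the groups are operational taxonomic unit (OTU) richness (number of unique bacteria) and Shannon Index", as measures of alpha diversity. Beta diversity "is assessed using PCA plots with Hellinger transformation or Principal Bray-Curtis", and heatmaps are added.
- **Summaries.** "Numerical parametric data is given as mean +/- SD while non-parametric data is given as median and range".
- **Decision rule.** "For all variables, p-values will be calculated and values <0.05 are significant". The data listed for analysis just before this include demographic and descriptive patient data, the three microbiomes and the rUTI results.

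Under Number of patients for inclusion, the protocol says "The number of women to be included to achieve a sufficient number in relation to strength calculation is therefore difficult to estimate". It then refers to other studies: "it is planned to include 100 women in total". It states no effect size, SD, event rate or power.

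Under Study design: "The study program is designed as a prospective, double-blind, randomized case-cross over study", with two three-month treatment periods. The background and the Research ethics section both justify the cross-over by large differences between women and stability within a woman. Publication of results commits the team to publishing whether results turn out positive, negative or inconclusive.

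**The concern.** The design exists to estimate a difference within each woman. The analysis section asks for no such difference and no measure of its precision. It asks for summaries of the outcome, whose SD includes the large spread between women that the cross-over is meant to remove, and for a verdict at 0.05.

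A threshold sorts results into two classes, while the publication plan names three. What separates a negative result (effects of interest ruled out) from an inconclusive one (effects of interest still possible) is the interval. Without it, and with no stated power, a reader who sees p above 0.05 cannot tell from the planned output how large an effect remains possible. This is most acute for UTI prevention, the secondary objective and the result most likely to influence practice.

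**Working it through.** **The plan's own figure.** The 100 women cannot be reproduced, because no effect size, SD, event rate or power is given. The check is therefore what 100 women would deliver, taking 0.05 as two-sided (an assumption; the protocol does not say).

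**1. Diversity measures, paired.** The 95% half-width, in units of the SD of the within-woman difference, is 1.96/√n.

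- n = 100: 1.96/10 = 0.196, or about 0.20 SD.
- Detectable with 80% power: (1.96 + 0.84)/10 = 0.28 SD.
- Power for a true 0.2 SD difference: Φ(0.2 × 10 − 1.96) = Φ(0.04) = 52%.

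The protocol replaces drop-outs only in the first three months ("If there are drop out during the first 3 months, a similar number to the drop out will be included"), so complete pairs may be fewer. With 80 pairs (assumed), the half-width is 1.96/√80 = 0.22 SD.

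**2. Can a reader recover that interval from the group SDs?** If both treatments have the same SD, SD(difference) = SD × √(2(1 − ρ)), where ρ is the within-woman correlation. The planned output does not include ρ. Over an assumed range, with n = 100:

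| ρ | SD(difference) / group SD | Half-width in group SDs |
|---|---|---|
| 0 (pairing ignored) | 1.41 | 0.28 |
| 0.2 | 1.26 | 0.25 |
| 0.5 | 1.00 | 0.20 |
| 0.8 | 0.63 | 0.12 |

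The same group SD is compatible with half-widths that differ more than twofold. A median and range does not give even this much.

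**3. UTI rate ratio (secondary outcome).** The event rates are assumptions taken from the entry criteria under Subjects: three UTIs a year is 3/4 = 0.75 per three months, and two in six months is 2/2 = 1.0. With e0 and e1 the UTIs on placebo and on Femidur, SE(log ratio) = √(1/e0 + 1/e1), and the interval is ratio × exp(±1.96 × SE). Under Poisson counts with equal time on each treatment, stable differences between women cancel.

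- True null, rate 0.75: 75 v 75 UTIs, SE = √(2/75) = 0.163, interval 0.73 to 1.38.
- True null, rate 1.0: 100 v 100 UTIs, SE = √(2/100) = 0.141, interval 0.76 to 1.32.
- Observed ratio 0.75, rate 0.75: 75 v 56.25 UTIs, SE = √(1/75 + 1/56.25) = 0.176, interval 0.53 to 1.06.
- Observed ratio 0.75, rate 1.0: 100 v 75 UTIs, SE = √(1/100 + 1/75) = 0.153, interval 0.56 to 1.01.

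Power for a true ratio of 0.75 is Φ(|ln 0.75|/SE − 1.96). This is Φ(0.288/0.176 − 1.96) = 37% at the lower rate and Φ(0.288/0.153 − 1.96) = 47% at the higher.

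Entry thresholds describe past history, and rates on trial may be lower. At 0.5 per three months, a ratio of 1.0 has SE = √(2/50) = 0.200 and an interval of 0.68 to 1.48. At 0.25, SE = √(2/25) = 0.283 and the interval is 0.57 to 1.74. Drop-out and overdispersion would widen all of these.

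**The case against.** The strongest reply is that this is a reporting gap which closes itself. The data are collected either way, the named software (SPSS and R) gives intervals, and the authors may report them unprompted. If means are given by treatment, subtraction yields the point difference. With n and the SDs, a reader can form an unpaired interval, which is conservative if the within-woman correlation is positive, as the protocol's own rationale implies. The UTI figures concern a secondary outcome at assumed rates. For the diversity measures, a half-width of 0.20 SD of the difference is fairly informative.

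Much of this stands. No data are lost, and some information about effect can be recovered where means are reported. What remains is that the plan does not commit to the contrast its design was chosen for, the paired precision cannot be rebuilt, and skewed outcomes shown as median and range give neither the contrast nor its precision.

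A reader might also infer more than the documents support:

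- *That the authors will read p above 0.05 as no effect.* The protocol does not say so, and it lists inconclusive results as a separate class. It lacks only a rule for telling them apart.
- *That a p-value means nothing without a power calculation.* Its definition does not depend on one. What is missing is any stated sensitivity behind a non-significant result.
- *That a power calculation was declared impossible.* The protocol says the number is hard to estimate and relies on other studies.
- *That p-values and group summaries are the only outputs.* PCA plots and heatmaps are planned too, though they give neither effect size nor precision for the treatment comparison.

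**Conclusion.** The point holds as a defect in the stated decision rule and in what will be reported. It is not a finding that the trial is too small or that its authors will misinterpret it. The interval widths follow from the sample size, and reporting them makes them visible without changing them.

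For UTI, under Poisson counts, 100 complete pairs and 0.75 to 1.0 UTI per woman per three months, a null result would still leave open reductions of 24% to 27% and increases of 32% to 38%. At the lower rate, an observed 25% reduction would be non-significant while compatible with a 47% reduction. For OTU richness and Shannon Index, the precision is about 0.20 SD of the within-woman difference. That could support a reasonably informative negative conclusion, but only if the interval is shown.

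The change should be made: it bears on interpretation, and leaves data collection and safety untouched.

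**What to change.** Replace the p-value sentence under Statistical variables and data with:

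> For OTU richness, Shannon Index and UTI count, the within-woman Femidur–placebo difference (rate ratio for UTI), from a paired or mixed model with a period term, is reported with its 95% confidence interval and p-value. A non-significant result is interpreted from the interval and not as evidence of no effect. Baseline characteristics are described without p-values.

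Each period has two on-treatment visits (1.5 and 3 months, then 4.5 and 6 months), so the plan should also name the visit or visits that enter the diversity contrast. PCA plots and heatmaps stay descriptive, since a single difference with an interval does not apply to them. The baseline clause is needed because the current rule covers all variables, and testing baseline differences between randomised groups only tests chance.

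The cost is slightly more analysis work: a defined model in place of unspecified tests. No extra women, visits, samples or software are needed.

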made prior to the outpatient clinic visit with the women's general practitioner to confirm that the UTI is culture-verified. The same is done if it is during the woman's visit to the outpatient clinic that the suspicion of rUTI arises. In such cases, the woman can only be offered final inclusion once the diagnose rUTI have been confirmed by cultivation as earlier described. The women can instead be informed about the study and provided with written material.

The included women are allowed to take regular medication, except for long-term treatment with prophylactic antibiotics. They are not allowed to take probiotics.

If the women have a current UTI, this is treated in relation to culture responses. After that, the women can be included in the study. It is recorded if the women use systemic or topical estrogen, and the specific type is noted.

Inclusion and exclusion

Risks and side effects

The women are not expected to experience serious side effects or disadvantages in the study. Nor that any damage, short or permanent is caused.

Femidur® is a probiotic and not a medical product. This means that it consists of well-defined microorganisms. Femidur contains two lactobacilli; Lactobacillus rhamnosus GR-1® and Lactobacillus reuteri RC-14®, which are part of the normal flora in humans. There are no known side effects for Femidur®.

Protocol

Femidur® is a dietary supplement consisting primarily of plant gelatin, maltodextrin and lactobacilli (*Lactobacillus rhamnosus* GR-1® and *Lactobacillus reuteri* RC-14®). Maltodextrin are carbohydrates in the form of short and medium starch chains. It is found both in ordinary groceries and used in the pharmaceutical industry. None of the substances are likely to cause allergic reactions or side effects. Should discomfort or hypersensitivity reactions occur against the capsules, this will be recorded. If the women wish to leave their studies, they can always do so.

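### Safety recording is limited to reactions against the capsules, no described visit asks about complaints and no tolerability analysis is planned, so tolerability on Femidur and placebo cannot be reliably compared

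*Combined protocol and SAP*

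**What the plan says.** **Recording rule.** Risks and side effects contains the only rule: "Should discomfort or hypersensitivity reactions occur against the capsules, this will be recorded". It does not say who decides that a reaction is due to the capsules, when or how women are asked, on what form the reaction is entered, or whether the treatment period is noted. The same section states "There are no known side effects for Femidur" and "None of the substances are likely to cause allergic reactions or side effects".

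**Visits.** Study Setup and intervention describes each visit after baseline. All four collect urine, a vaginal swab and stool. In addition:
- 1.5 months: "The women fill out the ICIQ-OAB and ICIQ-UI-SF questionnaires".
- 3 months, before the switch of capsules: "They completed questionnaires like those filled in at the beginning, but only DWD for a period of one day".
- 4.5 months: the two ICIQ questionnaires ("They fill out the ICIQ-OAB and ICIQ-UI-SF questionnaires").
- 6 months: the two ICIQ questionnaires, a one-day diary and an assessment of the treatment's effect.

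No visit includes a question on side effects, other complaints or health-care contacts. Constipation is collected at inclusion only (Implementation, examination and extend of study).

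**Analysis.** Statistical variables and data lists patient descriptors, the three microbiomes and the rUTI results. Tolerability is not listed there, nor among the objectives in Purpose of the project.

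**Withdrawals.** Women may leave without giving a reason (Recruitment). Those who drop out in the first 3 months are replaced (Number of patients for inclusion).

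**The concern.** The rule is narrow in two ways. It covers only reactions attributed to the capsules, in a section that says none are known and none are likely. It also relies on the woman volunteering the complaint, because no visit asks. A bowel or skin complaint that she does not connect with the capsules falls outside the rule.

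Nothing later in the plan makes up for this. A woman who stops in the first period because the capsules disagree with her can leave without a stated reason and be replaced, with no tolerability record.

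What is at stake is useful information and some patient safety. Every woman has a blinded Femidur period and a blinded placebo period, so identical questions in both would give a placebo-controlled, within-woman description of tolerability at visits already scheduled. Under the present rule, a report of few or no side effects could not be told apart from a failure to ask.

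**Working it through.** The protocol gives no safety figure, so there is none to reproduce. The main check is a reading of the text, followed by an illustration of size.

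**Step 1: routes by which an event could enter the data.**

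| Type of event | Route described |
|---|---|
| Discomfort or hypersensitivity attributed to the capsules | Recorded, if it comes to light |
| Urinary infection | Trial outcome: trial card, culture at symptoms, urine culture at each visit, rUTI results analysed |
| Other complaint or illness not attributed to the capsules | None |
| Reason for stopping | Not required, and no record described |

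**Step 2: what zero recorded reactions would exclude.** From the protocol: n = 100 women. Assumed: a share c of true reactions is captured.

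If the true rate is p, the recorded rate is c × p. With zero recorded in n women, the one-sided 95% upper bound solves (1 − c × p)^n = 0.05, so p = [1 − 0.05^(1/n)] / c.

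- c = 1: 1 − 0.05^(1/100) = 2.95%
- c = 0.5: 2.95% / 0.5 = 5.9%
- c = 0.3: 2.95% / 0.3 = 9.8%

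**Step 3: effect on a Femidur–placebo contrast.** Exact two-sided McNemar test, 100 pairs, alpha 0.05. Assumed: responses independent within woman, the same capture c in both periods, no carry-over. With recorded rates f on Femidur and g on placebo, the discordant probabilities are f(1 − g) and g(1 − f).

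For assumed true rates of 25% and 10%:
- c = 1: 0.25 × 0.90 = 0.225 and 0.10 × 0.75 = 0.075, so about 30 discordant pairs are expected; power 75%.
- c = 0.5 (recorded rates 12.5% and 5%): 0.125 × 0.95 = 0.119 and 0.05 × 0.875 = 0.044, so about 16 discordant pairs; power 38%.

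For assumed true rates of 30% and 10%, power is 93% with full capture and 59% with half.

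The documents give neither capture rates nor reaction rates. Steps 2 and 3 show only how strongly any safety statement depends on capture, which the present rule leaves unknown.

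**The case against.** The best defence is that this is a blinded trial of a dietary supplement with no tolerability objective. The rule does commit to recording discomfort, a broad term. The women attend in person four times after baseline and can speak up. Reactions recorded under blinding can be tabulated by period, and under-capture that is equal in both periods does not by itself favour either one. All of this stands. It supports light safety collection and rules out any claim that the comparison is impossible. It does not supply a question at the visits, a recording procedure or a planned table.

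A reader might infer more than the documents support:
- **That the plan breaches its own duty to monitor the gut.** The background asks for monitoring of the intestinal microbiome, and stool samples at every visit do that. No duty to follow gut symptoms is stated.
- **That medical records are closed to the study.** "Information from the journal of the women is not used for the study" ends a paragraph on baseline data, while Subjects uses the hospital record system to confirm cultures. The sentence cannot carry that weight.
- **That a serious urinary infection would never be recorded.** Urinary infection is a trial outcome with several described routes. How outside results reach the trial is unclear, but that is a separate matter.
- **That the trial fails to test its own claim of safety.** "There are no known side effects for Femidur" reports prior knowledge and is not a hypothesis of the study.
- **That a blinded assessor screens events for cause.** No assessor is named. The text limits recording to reactions against the capsules and does not say who decides.

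The within-woman comparison also has its own weakness. No washout is described at 3 months, so carry-over could blur it.

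**Conclusion.** The point holds in a limited form. Recording as written is passive and restricted to reactions attributed to the capsules. The trial cannot reliably compare tolerability between the two periods and plans no such comparison. Illness that is neither attributed to the capsules nor a urinary infection has no described route into the data.

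The textual conclusion needs no numerical assumption. The size does: bounds of about 3% against 6% to 10% rest on an assumed capture of 30% to 50%, and the power figures also rest on assumed reaction rates. The project overview figure was not available for this check, but the written visit descriptions cover all five visits.

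The change should be made, because it improves safety information at little cost. It does not affect the validity of the microbiome or rUTI comparisons.

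**What to change.** Replace the recording sentence in Risks and side effects with a procedure, and add it to the visit descriptions:

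1. At 1.5, 3, 4.5 and 6 months, put the same open question and a short fixed list to every woman: bowel complaints, vaginal complaints, skin or allergic complaints, antibiotic courses, and doctor or hospital contacts since the last visit. At 3 months, ask before the new capsules are dispensed.
2. Enter every event in RedCap with start and stop dates, regardless of suspected cause.
3. When a woman stops, record the reason if she offers one, including women who are later replaced.
4. In Statistical variables and data, add a descriptive table of events by Femidur and placebo period and by sequence. The split by sequence is needed because second-period events in women who took Femidur first may reflect carry-over. State that these tables are exempt from the rule that p-values are calculated for all variables.

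The cost is a few minutes at each of four existing visits and one form, with no extra visit. The downside is that more minor, unrelated complaints will be recorded, so the safety summary may look slightly less favourable.
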